3.7.2. Analysis Visit Windows

Subject visits might not occur on protocol-specified days. Therefore, for the purpose of analysis, observations will be assigned to analysis windows.

The following windows (Table 3-1 to Table 3-5) apply to baseline and on-treatment assessments only. For summaries and analysis, assessments will first be categorized into baseline and on-treatment assessments occurring during the randomized CCI phase, before applying analysis windows.

For subjects who prematurely discontinued the randomized study drug CCI, laboratory assessments up to and including the last dose date of the randomized study drug + 3 days, and DXA assessments up to and including the last dose date of the randomized study drug + 14 days, will be considered as baseline or on-treatment during the randomized phase.

CCI

For subjects who have not discontinued the randomized study drug permanently, data collected up to database finalization date will be considered as baseline or on-treatment of the randomized phase.

CCI

CCI
 CCI

For subjects who discontinue study drug early due to HBsAg loss with confirmed seroconversion, all efficacy data including data collected after the last dose date of the study drug will be reassigned analysis visits using the on-treatment assessment windows (Table 3-1 and Table 3-3).

The analysis windows for HBV DNA, hematology, serum chemistry and liver function tests, eGFR (by CG and CKD-EPI), renal biomarkers urine albumin to creatinine ratio (UACR), urine protein to creatinine ratio (UPCR), renal tubular maximum reabsorption rate of phosphate to the glomerular filtration rate (TmP/GFR), urine fractional excretion of filtered phosphate (FEPO₄), fractional excretion of uric acid (FEUA), non-fasting glucose, weight, and vital sign assessments are provided in Table 3-1.

Table 3-1. Analysis Visit Windows for HBV DNA, Hematology, Serum Chemistry and Liver Function Tests, eGFR (by CG and CKD-EPI), UACR, UPCR, TmP/GFR, FEPO₄, FEUA, Non-fasting Glucose, Weight, and Vital Sign Assessments

Nominal Visit	Nominal Study Day	Lower Limit	Upper Limit
Baseline			1
Week 4	28	2	41
Week 8	56	42	69
Week 12	84	70	111
Week 20	140	112	153
Week 24	168	154	209
Week 36	252	210	293
Week 48	336	294	377 (419 ^b)

[figure not shown]
CCI
 CCI

^b Applies to UACR, UPCR, TmP/GFR, FEPO₄ and FEUA only.

The analysis window for Fasting Glucose, Serum Cystatin C and eGFR by CKD-EPI Cystatin C is in Table 3-2.

Table 3-2. Analysis Visit Windows for Fasting Glucose, Serum Cystatin C and eGFR by CKD-EPI Cystatin C

[figure not shown]
Nominal Visit	Nominal Study Day	Lower Limit	Upper Limit
Baseline			1
Week 4	28	2	55
Week 12	84	56	125
Week 24	168	126	251
Week 48	336	252	419

The analysis windows for BMD results from DXA, fasting and non-fasting lipid panel including direct low density lipoprotein (LDL), high density lipoprotein (HDL) and total cholesterol to HDL ratio, Fibrotest and HBV serology are presented in [Table 3-3](#).

Table 3-3. Analysis Visit Windows for BMD Results from DXA, Fibrotest, Lipid Panel and HBV Serology

Nominal Visit	Nominal Study Day	Lower Limit	Upper Limit
Baseline			1(14 ^a)
Week 24	168	2(15 ^a)	251
Week 48	336	252	503

a Applies to DXA only. Upper limit for baseline DXA BMD is Day 14 and lower limit for Week 24 DXA BMD is Day 15.

The analysis windows for Cr EDTA renal scan are presented in [Table 3-4](#).

Table 3-4. Analysis Visit Windows for Cr EDTA Renal Scan

[figure not shown]
Nominal Visit	Nominal Study Day	Lower Limit	Upper Limit
Baseline			1
Week 48	336	2	503

The analysis windows for renal biomarkers including urine retinol binding protein (RBP) to creatinine ratio, urine beta-2-microglobulin to creatinine ratio, and bone biomarkers including serum parathyroid hormone (PTH), C-type collagen sequence (CTX), procollagen type 1 N-terminal propeptide (P1NP), osteocalcin (OC), and bone specific alkaline phosphatase (bsAP) are presented in [Table 3-5](#).

Table 3-5. Analysis Visit Windows for Renal and Bone Biomarkers

Nominal Visit	Nominal Study Day	Lower Limit	Upper Limit
Baseline			1
Week 4	28	2	55
Week 12	84	56	125
Week 24	168	126	251
Week 48	336	252	419

Data collected after the last dose date will be considered as post-treatment visits. The analysis windows for post-treatment assessments are presented in [Table 3-6](#).

Table 3-6. Analysis Visit Windows for Post Treatment Assessments

Nominal Visit	Nominal Study Day	Lower Limit	Upper Limit
Follow-Up Week 4	28	4	41
Follow-Up Week 8	56	42	69
Follow-Up Week 12	84	70	97
Follow-Up Week 16	112	98	125
Follow-Up Week 20	140	126	153
Follow-Up Week 24	168	154	181

3.7.3. Selection of Data in the Event of Multiple Records for an Analysis Visit Day

Depending on the statistical analysis method, single values are required for each analysis window. For example, change from baseline by visit usually requires a single value, whereas a time-to-event analysis would not require 1 value per analysis window. When a single value is needed, the following rule(s) will be used.

For baseline of the randomized phase, the last available record on or prior to the first dose of study drug will be selected. For DXA BMD, it is defined as the last value on or prior to Study Day 14. If there are multiple records with the same time or no time recorded on the same day for numeric observations, average will be computed for that day. If there are multiple records with the same time or no time recorded on the same day for categorical observations, the most conservative value will be taken, eg, negative will be selected over positive for HBeAg and HBsAg, and positive will be selected over negative for HBeAb and HBsAb.

The following specified rules will be used for postbaseline visits:

- **Alanine aminotransferase (ALT):** The largest value will be included in the analysis when 2 or more ALT values occur within the same visit window.
- **BMD:** The latest record in the window will be selected.
- **HBV DNA (IU/mL):** The record closest to the nominal day for that visit will be selected. If there are 2 records equidistant from the nominal day, the latest will be selected. If there is more than 1 record on the selected day, the geometric mean will be taken.
- **Serology:** For HBeAg, HBeAb, HBsAg, and HBsAb, the record closest to the nominal day for that visit will be selected. If there are 2 records equidistant from the nominal day, the latest will be selected. If there is more than 1 record on the selected day, the most conservative value will be taken, ie, positive will be selected over negative for HBeAg and HBsAg, and negative will be selected over positive for HBeAb and HBsAb.

For all other laboratory parameters:

- If multiple valid non-missing **numeric** observations exist in a window, then records will be chosen as follows:
 - The record closest to the nominal day for that visit will be selected. If there are 2 records equidistant from the nominal day, the latest will be selected. If there is more than 1 record on the selected day, the average will be taken.
- If multiple valid non-missing **categorical** observations (eg, safety ECG results) exist in a window, then records will be chosen as follows:
 - The most conservative value (eg, abnormal will be selected over normal for safety ECG) within the window will be selected. In the event that 2 values within a window are of equal abnormality, the value collected nearest to the nominal date will be used.

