## 6.5. Assessments for Premature Discontinuation from Study

If a subject discontinues study dosing (for example, as a result of an AE), every attempt should be made to keep the subject in the study and continue to perform the required study-related follow-up and procedures (see Section 6.6, Criteria for Discontinuation of Study Treatment). If this is not possible or acceptable to the subject or investigator, the subject may be withdrawn from the study.

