#### 7.5.5.2. For subjects on TAF:

- If the eGFRCKD-EPI is confirmed to be  $\geq 15$  mL/min/1.73 m^2, no dose modifications are required

7.5.5.3. For subjects on TAF or TDF:

- All subjects with a confirmed  $eGFR_{CKD-EPI} < 15 \text{ mL/min/1.73 m}^2$  will be required to permanently discontinue treatment
- All subjects with a change from baseline serum creatinine of  $\geq 0.4 \text{ mg/dL}$  must have serum creatinine repeated, with a concurrent urinalysis and urine chemistry, within two weeks of receipt of results

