## **8.3. Data Handling Conventions**

For the primary endpoint missing data will be handled using a missing = failure approach, unless otherwise specified.

For key secondary safety endpoints, an analysis will be performed using the Last Observation Carried Forward (LOCF) method to impute the missing data.

For other categorical secondary efficacy endpoints, missing data will be handled using a missing = failure approach. For the drug resistant mutations endpoint, a missing = excluded approach will be employed.

Sensitivity analyses will be performed as warranted.

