3.5. Missing Data and Outliers

3.5.1. Missing Data

In general, missing data will not be imputed, unless methods for handling missing data are specified. Exceptions are presented in this document.

A missing baseline laboratory result will be treated as normal (ie, no toxicity grade) for the laboratory abnormality summary.

Both baseline and postbaseline borderline results for HBeAg, hepatitis B e antibody (HBeAb), HBsAg, and hepatitis B surface antibody (HBsAb) will be imputed as follows:

- HBsAb/HBeAb borderline → HBsAb/HBeAb negative
- HBsAg/HBeAg borderline → HBsAg/HBeAg positive

For missing last dosing date of study drug, imputation rules are described in Section 4.2.1. The handling of missing or incomplete dates for AE onset is described in Section 7.1.6.2, and for prior and concomitant medications in Section 7.7.

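### Subjects who stop early, including mandatory renal stops, have no eGFR value in the Week 24 or Week 48 change summary, and no sensitivity summary is planned for them

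*SAP*

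**What the plan says.** The primary safety endpoint is the change from baseline in eGFR (CKD-EPI) at Week 24; Week 48 is secondary (Protocol 3.1). Both are summarized descriptively.

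**Stopping rule.** Protocol 6.6 and 7.5.5.3 apply to both arms: a subject with confirmed eGFR below 15 "will be required to permanently discontinue treatment". Protocol 6.5 asks that, after a stop, "every attempt should be made to keep the subject in the study and continue to perform the required study-related follow-up and procedures".

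**Which values count.** SAP 3.7.2 says its visit-window tables for baseline and treatment "apply to baseline and on-treatment assessments only". After a premature stop, on-treatment laboratory data are "laboratory assessments up to and including the last dose date of the randomized study drug + 3 days". Beyond that, "Data collected after the last dose date will be considered as post-treatment visits", with windows of their own in Table 3-6. The Week 24 row of Table 3-1, which covers CKD-EPI eGFR, reads "Week 24 168 154 209" (nominal day, lower limit, upper limit). The Week 48 window opens on Day 294. One exception lets data after the last dose back into the on-treatment windows: efficacy data after HBsAg loss with seroconversion. It does not reach eGFR.

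**Missing values.** SAP 3.5.1: "In general, missing data will not be imputed, unless methods for handling missing data are specified". SAP 7.4.3 specifies no method for eGFR. Protocol 8.3 says "For the primary endpoint missing data will be handled using a missing = failure approach", subject to other specification, and plans a last-observation-carried-forward (LOCF) analysis for key secondary safety endpoints, without defining key. Protocol 8.6.5 summarizes selected laboratory data as observed.

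**The concern.** The variable that triggers the stop is the variable being summarized. A subject whose eGFR falls below 15 early in the study leaves the Week 24 change summary because of that fall. The remaining subjects' mean then describes those who did not reach the renal limit. If such stops differ between arms, the arm with more of them will usually show the smaller mean decline.

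No other rule brings these subjects back into that summary. Missing = failure suits a proportion, and SAP 6.1.2 applies it to HBV DNA; a continuous change has no failure category. The protocol's LOCF analysis does not extend to the primary safety endpoint. It could cover eGFR at Week 48, a listed secondary safety endpoint, if that counts as key. The SAP does not carry LOCF over, however: the term stands only in its abbreviation list. SAP 7.9, which records changes from the protocol's safety analyses, does not mention the omission.

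Early renal stops are possible in this population. Only a screening eGFR below 15 excludes a subject (Protocol 4.3), and about 40 of 50 subjects are to enter with eGFR below 60. With about 25 per arm and no formal test, the descriptive summary is the primary safety result, and one or two subjects can move its mean.

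**Working it through.** The documents give no sample size calculation, SD or expected number of stops, so there is no figure of the plan's own to reproduce. Two checks apply.

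**Check 1: which stops lose the value.** A value is possible only if last dose day + 3 ≥ the day the window opens (154 for Week 24, 294 for Week 48; SAP Table 3-1).

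| Last dose (day) | Last usable lab (day) | Week 24 value possible? |
|---|---|---|
| 28 (Week 4) | 31 | No |
| 56 (Week 8) | 59 | No |
| 84 (Week 12) | 87 | No |
| 140 (Week 20) | 143 | No |
| 150 | 153 | No |
| 151 | 154 | Yes |
| 168 (Week 24) | 171 | Yes |

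For Week 48, 290 + 3 = 293 is too early and 291 + 3 = 294 is just in time. The cut-offs are therefore a last dose on or before Day 150 and Day 290. A stop prompted by the Week 24 visit itself keeps its Week 24 value.

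**Check 2: how far one subject moves an arm mean.** Let n = 25 (SAP 1.2), k = subjects lost, b = their baseline eGFR, m = mean change in the rest of the arm, and 14 = their last value. The values of k, b, m and 14 are assumptions; 14 is chosen to lie just under the stopping limit. The observed-only mean is m. Putting the last value back changes it by

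((25 − k)·m + k·(14 − b))/25 − m = k·(14 − b − m)/25.

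With k = 1 and m = −2:

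- b = 20: (−6 + 2)/25 = −0.16
- b = 30: (−16 + 2)/25 = −0.56
- b = 45: (−31 + 2)/25 = −1.16
- b = 60: (−46 + 2)/25 = −1.76

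With k = 2 these double, to between −0.32 and −3.52. With k = 1 and m varied from 0 to −5, the extremes are (−6 + 5)/25 = −0.04 and (−46 + 0)/25 = −1.84. All are in mL/min/1.73 m².

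The direction depends on baseline. Omission flatters the arm when 14 − b < m, that is when b > 14 − m. For m = −2 this means a baseline above 16; for m = −5, above 19. A subject who enters barely above 15 moves the mean very little either way.

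**How likely is at least one such stop?** The rate is unknown. For assumed rates p of 1%, 2%, 4% and 8%, 1 − (1 − p)^25 gives 22%, 40%, 64% and 88% for an arm of 25.

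**The case against.** Several points on the other side hold.

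- **These subjects are not lost from the report.** A reader might infer that renal stops disappear altogether. They do not. Their on-treatment values enter earlier visits, the counts of ≥ 25% and ≥ 50% eGFR decrease (SAP 7.4.3), confirmed renal abnormalities (7.4.1) and the reasons for stopping by arm (4.1). What is affected is the by-visit change summary. However, the confirmed-abnormality threshold is 30, the CKD-stage tables are by visit and so have the same gap, and no planned output counts stops under the below-15 rule.
- **Observed data is a stated convention.** Protocol 8.6.5 says so for laboratory data, and the missing = failure sentence allows for other specification. So the plan does have a rule for eGFR. Protocol 8.3 also allows sensitivity analyses as warranted, but neither document names one for eGFR.
- **The mean is not the only statistic.** Medians are reported, and the eGFR plots show median and quartiles, which one or two subjects barely move.
- **The Phase 3 result is not a usable yardstick.** A reader might set the shift against the 4.2 mL/min difference in Protocol 1.2.3 (−1.2 versus −5.4). That is a difference in medians of Cockcroft-Gault eGFR at Week 48 in a different population, so the ratio would mean little.
- **Off-treatment data may be unequal by arm.** Protocol 6.4.1 schedules treatment-free follow-up only for subjects who received TAF and ends it when other HBV therapy begins. This rules out an all-values summary as the main remedy.
- **One source is missing.** The Week 24 analysis was run under a separate SAP dated 19 March 2018, which is not among the documents, and part of SAP 3.7.2 is redacted. The final SAP says it reproduces all of that analysis except PK, so its rules are the ones read here.

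**Conclusion.** The point stands, limited to the change-from-baseline eGFR summaries at Weeks 24 and 48. Any subject whose last dose is on or before Day 150 (Day 290 for Week 48) contributes nothing to the corresponding summary. This holds for every kind of early stop. Renal stops matter most, because there the loss depends on the endpoint.

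The size is an assumption, not a finding. One such subject moves a 25-subject arm mean by about 0.2 to 1.8 mL/min/1.73 m² for baselines of 20 to 60, a last value of 14 and a mean change of −2 in the others. The documents do not say that any such stop occurred or that the arms differed, so they do not show that the reported result is biased. The study is exploratory and descriptive, so no error rate or power is at stake. What is missing is a low-cost check on the primary safety summary, together with a record in the SAP of why the protocol's LOCF analysis was left out.

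**What to change.** Keep the on-treatment summary as planned. In SAP 7.4.3:

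1. Add a sensitivity summary of Week 24 and Week 48 change in eGFR (CKD-EPI, creatinine). For subjects who stopped early and have no value in the window, carry forward the last available value up to and including the early discontinuation visit, by the same rule in both arms.
2. Report by arm the number stopped under the eGFR < 15 rule and the number carried forward at each time point.
3. Show later off-treatment eGFR only as a supplement, because scheduled follow-up after a stop differs by arm.

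In SAP 7.9, state what became of the protocol's LOCF analysis and which endpoints it was meant to cover. SAP 1 provides for changes after finalization to be documented in the clinical study report.

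The cost is one extra table from data the schedule already collects, since Appendix 2 of the protocol lists eGFR at the early discontinuation visit. The drawback is that a carried-forward value may not equal the true Week 24 or Week 48 value, so the table should be read beside the observed summary, not in place of it.

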4. SUBJECT DISPOSITION

4.1. Subject Enrollment and Disposition

Key study dates (first subject screened, first subject randomized, last subject randomized, last subject last visit for the primary endpoint, and last subject last visit for the clinical study report) will be provided.

The number and percentage of subjects enrolled in each randomization stratum will be summarized based on interactive voice response system/web response system (IXRS) data. If there are discrepancies between IXRS and screening laboratory data with regard to stratum assignment, a listing of the discrepancies will be provided.

The summary of subject disposition will be provided by treatment group and overall. This summary will include the number of subjects screened, screen failure subjects who were not randomized, subjects who met all eligibility criteria and were not randomized, subjects in the Randomized Analysis Set, subjects randomized but not treated, subjects in the Safety Analysis Set. **CCI** [REDACTED].

Study Drug Completion

- Prematurely discontinued randomized study treatment (with summary of reasons for discontinuing treatment)
- Completed randomized study treatment

- **CCI** [REDACTED]

- [REDACTED]

- [REDACTED]

Study Completion

- Entered 24-week treatment-free follow-up period
- Prematurely discontinued study (with summary of reasons for discontinuing study)
- Completed protocol-planned duration of the study

No inferential statistics will be generated. A data listing of reasons for premature study drug/study discontinuation will be provided.

4.2. Extent of Study Drug Exposure and Adherence

Exposure data described below will be summarized for the randomized phase CCI

4.2.1. Duration of Exposure to Randomized Study Drug

Duration of exposure to randomized study drug will be defined as (last dose date of randomized study drug – first dose date of randomized study drug + 1), regardless of temporary interruptions in study drug administration, and will be expressed in weeks (recorded to 1 decimal place, eg, 4.5 weeks). If subjects are still on randomized study drug, the latest of randomized study drug start and end dates, and the clinic and laboratory visit dates (excluding the CCI treatment-free follow-up visit dates) will be used to impute the last dose date of randomized study drug for calculating the duration of randomized study drug exposure.

Duration of exposure to randomized study drug will be summarized using descriptive statistics (sample size, mean, SD, median, Q1, Q3, minimum, and maximum) and as the number and percentage of subjects exposed for specified periods, eg, ≥ 4 weeks (28 days), ≥ 8 weeks (56 days), etc.

Summaries will be provided by treatment group for subjects in the Safety Analysis Set. No inferential statistics will be provided.

4.2.2. Adherence to Randomized Study Drug

Study drug regimen adherence will be computed based on tablet counts for the TAF group only. The numbers of tablets of study drug dispensed and returned are captured on study drug accountability forms.

Adherence (%) of study drug regimen will be calculated as follows:

$$\begin{aligned} \text{Adherence (\%)} &= 100 \times \frac{\text{Number of tablets taken}}{\text{Number of tablets prescribed}} \\ &= 100 \times \frac{\sum \text{No. of tablets taken at each dispensing period [1]}}{\sum \text{No. of tablets prescribed at each dispensing period [2]}} \end{aligned}$$

[1] Number of tablets taken at a distinct dispensing period for a study drug is calculated as the minimum of (a) the daily number of tablets prescribed for the study drug multiplied by **the duration of treatment** at the dispensing period of the same dispensing date, and (b) the number of tablets taken for the study drug (number of tablets dispensed minus the number of tablets returned). Total number of tablets taken is determined by summing the number of tablets taken from all evaluable dispensing periods.

[2] Number of tablets prescribed at a distinct dispensing period for a study drug is calculated as the daily number of tablets prescribed for the study drug multiplied by **the duration of treatment** at the dispensing period of the same dispensing date. Total number of tablets prescribed is determined by summing the number of tablets prescribed from all evaluable dispensing periods.

The duration of treatment at a dispensing period for a study drug is calculated as the minimum of (a) the last returned date of the same dispensing period for the study drug, (b) date of premature discontinuation of the study drug, and (c) **next dispensing date** of the study drug, minus dispensing date of the study drug.

The next dispensing date is the following dispensing date of the study drug regardless of the bottle return date.

For a record where the number of tablets returned was missing (with “Yes” answered for “Was bottle returned?” question), it is assumed the number of tablets returned was 0. If the number of tablets dispensed was missing or any study drug bottle was not returned or the bottle return status was unknown for the same dispensing date, then all records for the same dispensing date for that study drug will be excluded from both denominator and numerator calculation.

Adherence up to Week 48 visit will be calculated for each subject for the entire randomized dosing period up to the date of permanent discontinuation of the randomized study drug for subjects who prematurely discontinued randomized study drug or completed randomized study drug or using all data available for subjects remaining on randomized study drug.

The number and percentage of subjects who return at least 1 bottle and have calculable adherence during the study, descriptive statistics for adherence up to Week 48 visit for a study drug regimen (sample size, mean, SD, median, Q1, Q3, minimum, and maximum) along with the number and percentage of subjects belonging to adherence categories (eg, < 80%, ≥ 80% to < 90%, ≥ 90% to < 95%, ≥ 95%) will be provided by treatment group for the Safety Analysis Set. No inferential statistics will be provided.

CCI [REDACTED]

[REDACTED]

[REDACTED]

[REDACTED]

CCI

[REDACTED]

[REDACTED]

[REDACTED]

[REDACTED]

[REDACTED]

[REDACTED]

[REDACTED]

